We seek to make an effective psychoeducation program widely available to family caregivers of persons living with Alzheimer's disease and related disorders. Taking advantage of the growing use of and familiarity with the internet by persons of caregiving age, the project will advance us toward that goal. We will test the program in an established context of collaboration among the Outreach, Recruitment, and Education Cores of four NIA-supported Alzheimer's Disease Centers (ADC). We will employ a wait-list randomized design in which 18 blocks of 15 caregivers each will be assigned either to immediate Tele-Savvy participation groups or to attention control or usual care groups that are invited to participate in Tele-Savvy six months after baseline data collection (total n=270). We will pursue 3 aims::

Aim 1. Establish the effectiveness of Tele-Savvy in reducing or retarding the affective impact (burden, depression, anxiety) on caregivers associated with dementia family caregiving

Aim 2. Establish the effectiveness of Tele-Savvy in promoting the quality of life of persons with Alzheimer's (agitation; Quality of Life; affect) whose caregivers are trained by Tele-Savvy

Aim 3. (a) Establish the effectiveness of Tele-Savvy in enhancing caregiver mastery and (b) test the mediating effect of mastery and enactment on Aim 1 & 2 outcomes

We also propose, as an Exploratory Aim, to examine the comparability of the program's efficacy across three racial/ethnic groups (African Americans, Caucasians, and Latino/Hispanics).

Significance and Innovation.

The Landscape. Dementing conditions, including the most prevalent of these, Alzheimer's disease, pose a large and growing problem nationally and worldwide. Unless dramatic breakthroughs occur, the current population of 5.3 million persons living with these conditions will swell to at least 14 million by 2050.¹ These persons are distributed across the landscape, in inner cities, in suburban areas, and in rural America; there is even some evidence that the current and future prevalence of Alzheimer's in rural areas is disproportionate to the rural population's share of the overall population.²⁻⁴ Care for these persons is costly. Total estimated cost of care in 2015 will be \$216 Billion; by 2050, it could exceed \$1 Trillion.¹

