meta-analyses. With a final expected sample size of 215 (86, 86, 54 in Tele-Savvy (TS), attention control (AC), and usual care (UC) groups respectively), for the primary intervention test (group-by-time effect) comparing the outcomes of the three group changes from T1 to T2 to T3 (3-by-3 repeated measures design of three groups measured at three time points), at 80% power and 5% significance level, small-to-moderate effect sizes, Cohen's $f = 0.21-0.24$ may be detected for the main effects for group, time and group-by-time interaction effects (given moderate correlation between measurement pairs of $r=0.3-0.5$) (power analysis using PASS 14 Power Analysis and Sample Size Software (2015). NCSS, LLC. Kaysville, Utah, USA, ncss.com/software/pass). After adjusting for any potential group differences, the overall intervention effect of the Tele-Savvy program for the combined T1-to-T3 pre-post effects for the immediate Tele-Savvy group plus the T3-to-T5 pre-post effects from the AC and UC groups will yield a total estimated 215 subjects to perform a pre-post test to detect a small effect size of $d=0.19$ at 80% power and 5% significance level. With the pooled sample, we will be able to also test the mediating effects of mastery and self-efficacy on the Tele-Savvy program for the caregiver outcomes. As shown by Fritz and MacKinnon (2007), sample sizes of 148-196 were adequate to achieve 80% power to detect small-to-moderate effect sizes for the indirect effect of the independent variable on the dependent variable through the mediating variable considering both the Sobel test as well as percentile and bias-corrected bootstrapped approaches.¹⁰⁸ Although our analytic strategy is robust to missing data we will enroll 270 CGs (108 for TS and AC groups and 54 for UC group) per consideration 1 above (maximize accommodation) allowing for an expected 20% attrition. For the exploratory aim comparing the program's efficacy across the 3 ethnicity groups, with an expected final sample size of 215 subjects and proportions of approximately 65% Caucasian, 20% African American, 15% Hispanic, at 80% and 5% level of significance, we will be able to detect moderate effect sizes Cohen's $f=0.19-0.23$ (for 3-group by 2-time point RM-ANOVA for group, time and group-by-time effects).

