Care Recipient Mood	Neuropsychological Inventory Questionnaire	12 item inventory assessing severity of mood states or behaviors reflecting mood	Test-retest correlations between total symptom and distress scores in 15 subjects were 0.80 and 0.94, respectively (P< 0.0001 for both). ¹²¹

Data Collection. Data will be collected at baseline and at four subsequent points (months 3, 6, 9, and 12). Each data collection event will follow the same procedure used with the baseline interviews. The Navigator will establish the appointment for the Vidyo interview, and the research specialist, blinded to condition, will conduct the interview. The data collection schedule allows for a direct comparison of outcome measures between groups (at 3 and 9 months); it allows for an examination of prolonged effects (at 9 and 12 months) in the immediate participation group; and it allows for pooling of data across both groups to examine the mediating effects of mastery on distal outcomes in caregivers and PLWD and to compare effects across racial/ethnic groups. Qualitative evaluation interviews will occur at T2 and T3 for a sub-sample of immediate and T4 and T5 for a sub-sample of attention control subjects.

III. G. Variables and Measures. The table above delineates the battery of standardized instruments we will employ; these have well-established psychometric properties (reliability, validity), are used extensively with dementia caregivers, and have been used previously in the *Savvy Caregiver* trials.

As depicted in the figure below, there is a link between our theoretical model and the measures used to test it. Most data will be gathered through the regular interviews, some data will be obtained from self-reported evaluations that caregivers will complete through forms posted on the Canvas site (for example, through logs on the Canvas site in which caregivers report caregiving behaviors they have enacted). After each program, caregivers will be asked, in phone or Vidyo interviews conducted by project investigators, to evaluate the program, indicating what they did/did not like, what did/did not work, how the intervention was helpful or not, and how they would change it. Blackboard will allow us to monitor adherence, dosage and intensity of the

[figure not shown]

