data captured at T1-T2-T3 for the delay group will also be used to evaluate any potential decline occurring during this time period. All model assumptions will be tested; grand mean centering used to help combat multicollinearity between variables; and standard diagnostic tests and influence statistics used to test the distributions of the residuals. MLM models utilize all available data for all participants at each time point and have the advantage of adjusting for the missing data over time, where repeated measures ANOVAs do not. Further covariate predictors of missingness over time will be included to additionally adjust for these confounders¹²⁴ To aid in final interpretation we will include the 95% confidence intervals around means by intervention group and time period. SPSS v.22 will be used for all analyses at the 5% significance level.¹²²

Aim 3(b). To test the mediating effect of mastery on Aim 1 & 2 outcomes, we will employ the PROCESS add-on module for SPSS¹²⁵ which includes performing the combined approaches of Baron and Kenney, the Sobel test, as well as semi-parametric estimation and testing of the Sobel test through bootstrapping. The focus will be on both the immediate (T2 for immediate Tele-Savvy group and T4 for attention control and usual care groups pooled together) and sustained (T3 for immediate Tele-Savvy group and T5 for attention control and usual care groups pooled together) effects of Tele-Savvy on the mediating measure of mastery on the Aim 1 and Aim 2 outcomes of caregiver burden, depression, anxiety, and dyadic relationship and PLWD BPSD, agitation, mood, and quality of life. These indirect/mediation effects will also be tested and evaluated using structural equation modeling via AMOS v.22.¹²⁶

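### Aim 3(b) promises mediation tests of mastery and enactment, but the analysis section models mastery alone and the power text names self-efficacy instead of enactment

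*Combined protocol and SAP*

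**What the plan says.** Five places in the combined protocol and SAP name the mediators:

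- **Aims, Aim 3(b):** the trial will "test the mediating effect of mastery and enactment on Aim 1 & 2 outcomes".
- **Power Analysis and Sample Size Determination:** the text says of the pooled data: "we will be able to also test the mediating effects of mastery and self-efficacy on the Tele-Savvy program for the caregiver outcomes". This names a different second mediator and mentions caregiver outcomes only.
- **Wait List Attention Control Group Condition and Participation:** the postulated mediators are mood, mastery and the quality of life of the care recipient.
- **Data Collection:** data are pooled "to examine the mediating effects of mastery on distal outcomes in caregivers and PLWD".
- **Data Management and Analysis Plan, Aim 3(b):** "To test the mediating effect of mastery on Aim 1 & 2 outcomes, we will employ the PROCESS add-on module for SPSS". The structural equation step refers back to the same effects: "These indirect/mediation effects will also be tested and evaluated using structural equation modeling via AMOS v.22".

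On measurement, Variables and Measures says that some data come "through logs on the Canvas site in which caregivers report caregiving behaviors they have enacted", given as an example. The instrument table assigns the Pearlin scales to mastery and has no row labelled enactment or self-efficacy. The nearest row to enactment is the Caregiver Assessment of Behavioral Skill (17 items, self-report), with the Ways of Coping Scale also related. Neither is given a mediator role. A figure linking the theory to the measures is mentioned but is not visible in the text available.

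**The concern.** The analysis does not deliver what the aim promises. An analyst who follows the Aim 3(b) analysis text fits mastery and stops, so the trial reports nothing on whether enactment carries the effect. Enactment is a substantive part of the theory: the description of the Savvy Caregiver Program presents carrying out effective caregiving strategies, together with mastery, as contributing to the well-being of both members of the dyad.

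Because the documents carry several mediator lists, the choice of which mediators count could be made after the data are seen. There is a secondary issue: leaving out a mediator that is related to mastery can distort the mastery estimate in some circumstances.

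**Working it through.** **1. The mediator lists side by side**

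| Place | Mastery | Enactment | Self-efficacy | Other |
|---|---|---|---|---|
| Aims, Aim 3(b) | yes | yes | no | none |
| Power Analysis | yes | no | yes | none |
| Attention control condition | yes | no | no | mood; care recipient quality of life |
| Data Collection | yes | no | no | none |
| Analysis, Aim 3(b) (PROCESS and AMOS) | yes | no | no | none |

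Mastery is the only mediator common to all five. Enactment appears in the aim and in no analysis. Self-efficacy appears in the power text and in no analysis.

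**2. What goes untested.** The Aim 3(b) analysis lists eight outcomes (four for the caregiver, four for the care recipient) at two time windows, immediate and sustained. That is 8 × 2 = 16 indirect effects for mastery, and none for enactment.

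**3. The plan's own figure.** The mediation tests rest on the pooled sample, stated as n = 215 with d = 0.19 detectable at 80% power and the 5% level (two-sided assumed).
- Normal approximation: 0.19 × √215 − 1.96 = 0.826, giving 79.6% power. The paired t-test gives 79.2%.
- Inverse: ((1.960 + 0.842)/0.19)² = 217.4, so 218 against 215.

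The figure reproduces, so the problem is not arithmetic. The cited range of 148 to 196 for mediation is described for a single mediating variable and comes without path coefficients, so it cannot be recomputed here. The plan gives no figure for a two-mediator model.

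**4. What omitting enactment does to the mastery path.** Let b1 and b2 be the effects of mastery and enactment on the outcome, each given the other. Let ρ be their residual correlation, with unit residual variances. A mastery-only model estimates b1 + ρ × b2. The documents give none of these values. With b1 = b2 = 0.3 assumed:

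| ρ | Mastery-only slope | Shift |
|---|---|---|
| −0.3 | 0.3 − 0.09 = 0.21 | −0.09 |
| 0 | 0.30 | 0 |
| 0.3 | 0.3 + 0.09 = 0.39 | +0.09 |
| 0.5 | 0.3 + 0.15 = 0.45 | +0.15 |

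A simulation (n = 215, 40% treated, treatment effects of 0.5 SD on both mediators, 2,500 runs) gave 0.21, 0.30, 0.39 and 0.45. The two-mediator model gave 0.30 each time.

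**5. The order matters.** Suppose instead that mastery leads to enactment with slope 0.3. The full effect of mastery is then 0.3 + 0.3 × 0.3 = 0.39, and the mastery-only slope of 0.39 is the right answer. The same number is biased under one causal order and correct under another. The documents do not settle which applies.

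**The case against.** The strongest reply is that this is loose wording. The theory section ends by summarising the outcomes as mediated by mastery, which is what the analysis models. Self-efficacy may be a near-synonym, since the program uses self-efficacy principles to build mastery. The unseen figure may map enactment to an instrument, and the battery already holds behavioral skill, coping and self-care scales. The Canvas logs are offered only as an example.

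Much of this is fair. It does not answer the main point: a figure mapping theory to measures might supply an instrument, but the Aim 3(b) analysis text would still have no model for enactment.

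Three stronger readings are tempting, and the documents do not support them:

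- **A reader might infer that the mastery effect is certainly inflated, by some 30% to 50%.** Those percentages are the assumed-input shifts at ρ = 0.3 and 0.5 (0.09/0.3 and 0.15/0.3). In the same simulation with no true mastery effect, the mastery-only model declared mediation in 23% and 54% of runs at those correlations, against 4% to 5% for the two-mediator model. The rate was 4% at zero correlation. All of this depends on unstated paths and on causal order. The simulation also compares treated with untreated people, whereas the Aim 3(b) analysis takes each arm after it has been offered Tele-Savvy and pools the two delayed arms. These are illustrations of a mechanism and not magnitudes for this plan.
- **A reader might infer that half of Aim 3 is lost.** It is half of Aim 3(b). Aim 3(a) has its own analysis.
- **A reader might infer that Canvas logs cannot be used across arms.** In the pooled analysis every arm has been offered the program and Canvas with it. The limit that remains is the lack of a pre-program value: Canvas orientation follows the baseline interview and allocation, and for usual care it follows the 6-month data point.

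**Conclusion.** The inconsistency stands on the text and needs no assumption. Enactment, one of two mediators in Aim 3(b), has no planned mediation test, against 16 indirect effects planned for mastery. The power text claims a self-efficacy test that has no labelled instrument and no model in the visible text; the one reservation is the figure that is not shown.

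Bias in the mastery indirect effect is possible but not established. It needs enactment to affect the outcome and to correlate with mastery for reasons other than lying downstream of it. It is zero at zero residual correlation and, for a beneficial enactment effect, reverses if the correlation is negative. The documents give no values, so neither size nor direction can be stated.

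The point limits what the trial can conclude about mechanism. It does not touch the effectiveness comparisons under Aims 1, 2 and 3(a). It should be corrected because the stated analysis contradicts a stated aim and the remedy is cheap.

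**What to change.** Use one mediator list in the Aims, Power Analysis, attention control, Data Collection and Aim 3(b) analysis sections. Then do one of the following.

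1. **Keep enactment.** Add it to the PROCESS and AMOS models in the Aim 3(b) analysis. Measure it with an interview instrument collected in all arms, for example the Caregiver Assessment of Behavioral Skill, the nearest one listed. State in advance whether it enters in parallel with mastery or in series after it, and why. Use the Canvas logs as supporting data only.
2. **Drop enactment** from Aim 3(b), so that the aim matches the analysis.

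In either case, remove self-efficacy from the power text or name its measure and model.

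The cost is wording and, under option 1, one more mediator from data already collected, with slightly wider intervals for each indirect effect. In the simulation above, joint-significance power for mastery was 93% with both mediators against 95% with mastery alone at correlation 0.3, and 90% against 94% at 0.5. These depend on the assumed inputs, and the mastery-only figures carry the shifted slope. Option 1 also doubles the specific indirect effects from 16 to 32, so the plan should say how they will be read together.

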Monthly team videoconferences will be conducted to discuss project progress, recruitment, data collection and analysis, and other issues. The Emory coordinating team will meet weekly. The site co-

investigators and [name] will also meet annually at the ADC Directors' meeting. Additional Data Safety Monitoring Board committee meetings will be held mid-year in years 2 and 3.

Scientific Approach

Design. We aim to enroll 375 subjects in 25 cohorts of 15 subjects each, starting in project month 9 (see project timeline). We expect to enroll, on average, four cohorts per quarter through project year 2 1/2. Recruitment of every 2 cohorts (30 participants total) is scheduled to take place every 6 weeks. We will use a three-arm design with participants randomly assigned on a 2:2:1 ratio to immediate participation in the Tele-Savvy intervention (N=108), immediate participation in an attention control condition (Healthy Living) (N=108), and a usual care condition (N=54). There will be five data-collection points evenly spaced across 12 months. Those in each cohort's intervention condition will take part in Tele-Savvy immediately following baseline data collection. Those in the attention control and usual care conditions will take part in Tele-Savvy after a delay of 6 months (following the 6-month data collection point). Below, we describe the preparation activities in which we will engage (facilitator training and material revisions) and then describe the trial itself. Four NIA-supported Alzheimer's Disease (Research) Centers will collaborate in recruitment, and Emory University will serve as the coordinating center. Emory will be responsible for randomization of subjects (recruits from all sites will be pooled together for randomization), for delivery and fidelity monitoring of the intervention and attention control condition, and for all data gathering and analysis.

Please see the added document for Amendment 8.

Project Timeline, by Quarters

Main Project Activities	Year 1				Year 2				Year 3				Year 4			
	1	2	3	4	1	2	3	4	1	2	3	4	1	2	3	4
Staffing; Training; Finalizing																
DSMB scheduled meetings		X			X				X				X			X
Enroll 18 cohorts (15 each) + Acquisition	30	60	90	120	150	180	210	240	270							
Data Collection																
Data Cleaning and Analysis																
Dissemination																

Preparation.

Attention Control Condition Materials Preparation. The attention control condition (see below) will involve the distribution of video and text materials on exercise and nutrition. These are largely be materials from the NIA Go4Life program. [name] has led the effort of selecting and sequencing the materials and has worked with Drs. [name] and [name] and the Project Director to format them into an internet-delivered program.

Finalization of these materials (curriculum development and mapping content for group, individual, and asynchronous elements) has occurred during the preparatory phase of this study. Go4Life content is well-developed and is pertinent to caregivers, however, it does not address caregiving issues the way Tele-Savvy Program does. Go4Life provides a motivational framework for a healthier lifestyle, methods to track commitment and improvement, and more than 60 tip sheets on activities, nutrition, health benefits and safety around which daily video modules will be built. Additionally, videoconferences will be developed to incorporate on-line group interaction for attention-control participants to match the time in videoconferences (but not the content) among Tele-Savvy participants.

Facilitator Training. Persons from a variety of backgrounds (nursing, social work, education, etc.) who have experience leading the in-person Savvy Caregiver program will facilitate the synchronous group components of the Tele-Savvy program. We will compile a facilitator's manual, based on the material from the Savvy Caregiver's trainer's manual (see Appendix B) used in the Tele-Savvy pilot and the Tele-Savvy syllabus that delineates the content of the synchronous group videoconferences (Appendix A). The manual will provide clear educational objectives, a time-linked agenda, and descriptions of (and supporting material for) the talks and exercises conducted in each session. A training program ([name] Caregiver train-the-trainer program modified for Tele-Savvy) will be used. The training will engage facilitators in practicing the methods and material covered in the videoconferences, and will help facilitators to tailor to the videoconference format the coaching skills essential to facilitating the development of caregiver self-efficacy. It will also focus on the development and maintenance of "connectedness;" in this on-line environment, the facilitator can rely less on

non-verbal cues and has to employ a more directive style to manage group dynamics, such as “calling on” individuals to report on their home activities or to determine if they have questions. One or more facilitators will be trained to conduct the videoconference component of the “Healthy Living” attention control condition. Drs. [name] and [name] will develop and conduct the training program for the attention control facilitator(s). As part of training, each facilitator will lead, as appropriate, a dry run of Tele-Savvy and the Healthy Living programs. The lead investigators will observe these dry runs, providing coaching and additional training, as needed. Former participants of the in-person Savvy Caregiver program will be invited to participate.

Facilitators will be assigned to lead cohort-based Tele-Savvy groups based on their time availability; the leader will be consistent across the seven sessions of the cohort’s participation. No facilitator will ever lead more than two groups at a time. Over the course of the project, the investigators and the Project Coordinator will monitor Tele-Savvy and Healthy Living fidelity by observing and evaluating ≥ 3 individual group sessions per facilitator per cohort using a fidelity checklist. Fidelity will be evidenced by $\geq 80\%$ adherence to a group session compliance checklist. (Appendix D) Compliance ratings $< 80\%$ and median caregiver ratings for session quality of < 8 will signal [name] and [name] to discuss with facilitators, conduct PRN remedial training and observe/participate in the next two sessions or until ratings adherence is achieved and maintained.

Facilitators will be hired part-time or as consultants as a way to demonstrate that fidelity to the Tele-Savvy Program curriculum can be maintained across interventionists. Additionally, working with part-time facilitators in this study will provide evidence on the feasibility of similar employment of facilitators in other settings, such that Tele-Savvy may be administered by employees of existing organizations (e.g., social workers) as a part of their preexistent job description rather than their sole responsibility. Such incorporation of Tele-Savvy administration into the whole job description is more likely to make Tele-Savvy adoptable in a variety of settings rather than reliance on full-time facilitators.

Materials Finalization. Tele-Savvy is ready for testing. Our preliminary work has established the 43-day structure of the program and its delivery mechanisms. We have updated introductions and select content in the daily videos to include minority experts and actors for case examples. A course syllabus will be provided to participants to allow them to see the course as a whole and to link specific parts of the curriculum to the Caregiver Manual (Appendix C). Note page copies of the Powerpoint slides used in the videoconferences and daily lessons will be provided. The guides to the use of the interactive communication technology used in the program will be upgraded, based on our pilot experiences. Materials from the NIA website for Go4Life has been adapted for use in the attention control condition (see below). We will be placing the Tele-Savvy and attention control material on two commercially available platforms (Vidyo and Canvas) for which Emory has licenses and provides technical assistance. Both require little technical know-how by users; both are accessed by links provided via emails that we will send to participants.

Randomized Trial.

Subjects. Participants will be informal caregivers (family/friends) of persons living with Alzheimer’s disease or another dementia. Participants must be providing at least 4 hours per day unpaid assistance, on average, for a person in the early-middle stage of illness (Clinical Dementia Rating of ≥ 1 by home ADC) who is community-dwelling and for whom there is no established plan for institutionalization in the next six months. Caregiver may or may not reside with their care recipient, but care recipients must live in the community and not in an assisted living facility, nursing home, or another institutional setting. The participant must not be involved in another caregiver training study and must not have participated in in-person Savvy Caregiver Program or Tele-Savvy previously. Each participant must have access to a computer or a mobile device with adequate internet connection, microphone, and speakers (to be able to participate in teleconferences) and be able to use email (this was not a serious barrier in the pilot studies). Participants must be able to read, speak and understand English and have no uncorrectable vision or hearing deficits that might impede participation. Questions posed after explaining the project during eligibility determination and the consent process will be used to gauge caregivers’ cognitive ability to take part in the project. Webcams will be mailed to those caregivers who do not have them for the duration of the entire program and caregivers will be asked to mail webcams back after participation in Tele-Savvy.

Power Analysis and Sample Size Determination Several considerations enter into sample size determination: (1) our wish to accommodate as many caregivers as feasible given time/resources; (2) our experience and prior results from SCP trials; (3) sample and effect sizes/attrition rates in recent dementia CG

meta-analyses. With a final expected sample size of 215 (86, 86, 54 in Tele-Savvy (TS), attention control (AC), and usual care (UC) groups respectively), for the primary intervention test (group-by-time effect) comparing the outcomes of the three group changes from T1 to T2 to T3 (3-by-3 repeated measures design of three groups measured at three time points), at 80% power and 5% significance level, small-to-moderate effect sizes, Cohen's $f = 0.21-0.24$ may be detected for the main effects for group, time and group-by-time interaction effects (given moderate correlation between measurement pairs of $r=0.3-0.5$) (power analysis using PASS 14 Power Analysis and Sample Size Software (2015). NCSS, LLC. Kaysville, Utah, USA, ncss.com/software/pass). After adjusting for any potential group differences, the overall intervention effect of the Tele-Savvy program for the combined T1-to-T3 pre-post effects for the immediate Tele-Savvy group plus the T3-to-T5 pre-post effects from the AC and UC groups will yield a total estimated 215 subjects to perform a pre-post test to detect a small effect size of $d=0.19$ at 80% power and 5% significance level. With the pooled sample, we will be able to also test the mediating effects of mastery and self-efficacy on the Tele-Savvy program for the caregiver outcomes. As shown by Fritz and MacKinnon (2007), sample sizes of 148-196 were adequate to achieve 80% power to detect small-to-moderate effect sizes for the indirect effect of the independent variable on the dependent variable through the mediating variable considering both the Sobel test as well as percentile and bias-corrected bootstrapped approaches.¹⁰⁸ Although our analytic strategy is robust to missing data we will enroll 270 CGs (108 for TS and AC groups and 54 for UC group) per consideration 1 above (maximize accommodation) allowing for an expected 20% attrition. For the exploratory aim comparing the program's efficacy across the 3 ethnicity groups, with an expected final sample size of 215 subjects and proportions of approximately 65% Caucasian, 20% African American, 15% Hispanic, at 80% and 5% level of significance, we will be able to detect moderate effect sizes Cohen's $f=0.19-0.23$ (for 3-group by 2-time point RM-ANOVA for group, time and group-by-time effects).

Recruitment and Consent. To the extent possible, all sites will use existing research registries of PLWD and established community partnerships (e.g., with local Alzheimer's Association chapters or other community agencies) to identify caregivers who might be interested in the study. All study sites have robust recruiting networks and strong recruiting track records; we expect a diverse participant group with 25-40% minority (African American and Latino/Hispanic) participation. All of the ADCs have extensive outreach capacity, so we expect candidates will be identified at a distance from, as well as close to the Centers; this was the case in the Tele-Savvy pilots which drew participants from the Atlanta area but also from as far away as California, Minnesota, and Maine. We will employ the same enrollment and consent procedures as in the pilots. Caregivers will be informed about the study by the local coordinator or PI or, through referral, by Emory study staff. If interested, the person will be screened for eligibility by Emory staff (by asking potential subjects to repeat information provided about the study). Those eligible and still interested will be engaged in the consent process by Emory staff; the process will occur through a documented phone or video consent process.

Computer Set-up and Research Interviews. Cohorts will be composed of consented individuals from the study sites (i.e., the cohorts are not site-specific). Once a consented caregiver cohort has been identified, an Emory research specialist (termed a "navigator") will establish a time for a phone call to take him/her through the relatively straightforward steps of using email to follow URL links that open Vidyo, the videoconferencing application to be used in the project. Following this and while the navigator and participant are still on the phone, the navigator will send a test email to initiate a Vidyo conference with the person. [If we have had to send a webcam, the navigator will help the participant to install it.] During the videoconference, the navigator will guide the participant through practice in the use of the basic videoconference operations: accepting an incoming conference invitation; muting and unmuting the microphone; muting and unmuting the video camera; using the chat function; and ending the conference. At the end of this call, the navigator will schedule a time for a data collection call (done in person on Vidyo). These procedures were effective in the pilot.

A second Emory research specialist will make the data collection call, providing another opportunity to practice using Vidyo. All data collection will be done by a project research specialist at Emory, trained and supervised by the Emory Co-PIs. This specialist will have no other contact with the subjects and will be blinded to and will ask subjects not to discuss their study condition. For each instrument (or portion of each instrument), the interviewer will show the response options for the particular scale on the screen, so that the respondent does not have to keep those in mind (slides can be projected on the Vidyo platform). We used this procedure in the ADRC pilot project; it worked well and sped up the time of the interviews. Based on experience with the Tele-Savvy pilots, the research interview conference takes 40-60 minutes; it can extend over two calls, if necessary.

[figure not shown]
All patient records will be kept in a locked file cabinet in the research office at the School of Nursing (i.e. Wesley Woods) and will be accessible only to the PI and the research team.

Subject Randomization, Coordination, and Retention. Once a cohort of 15 consented subjects has been consented and interviewed, the study statistician ([name]) will use a block randomization scheme to assign equal numbers of members of the cohort to immediate Tele-Savvy or attention control or usual care wait-list participation. As the figure to the right illustrates, the three groups will each, over 12 months, get the Tele-Savvy program. Attention control program will be administered solely to participants who have been randomized to be in attention-control condition initially. Thus, participants who have been randomized to be in Tele-Savvy condition initially or to usual care will not receive attention-control intervention at 6 months post-baseline. Navigators will inform subjects of group assignment and will establish a schedule for participation. For immediate Tele-Savvy participants, start time and time of day for the videoconferences will be set. For those in attention control, start time and time of day for the videoconferences will be set likewise. For those in the usual care condition, an individual schedule of "empathetic calls" will be established. Videoconferences for both Tele-Savvy and attention control will be offered on weekdays (during business hours and evenings) and on weekends to facilitate participation for caregivers who may not be able to join videoconferences on weekdays. Caregivers who might be best served by a Saturday or an evening program will be placed into a block and randomly assigned to Tele-Savvy or attention control conditions. Caregivers for whom weekday participation is non-problematic will be allocated to conditions as described above.

After navigators inform caregivers about their condition assignment and establish a schedule for participation for those in immediate Tele-Savvy and attention control groups, navigators will conduct individual videoconferences to introduce them to Canvas, a widely used course management platform that will house the daily video lessons. Canvas allows participants to view video lessons at their own convenience and as often as they wish, but it does not allow them to disseminate them. It allows us to track individual use, so we can monitor the "dose" of each participant's viewing. Navigators will teach caregivers how to login and access materials in Canvas and will provide navigators' contact information, reinforcing that caregivers should contact navigators for technical assistance at any time. Canvas also allows us to post evaluation questionnaires. The videoconference will provide participants with another opportunity to practice with Vidyo and to practice opening the lessons (during their participation in Tele-Savvy, navigators will send emails to remind them to access the lessons). The procedure for orienting participants to Canvas will be provided to usual care group participants following the 6-month data collection point and prior to their entry to the Tele-Savvy program. In an effort to keep them engaged in the study, regardless of group assignment, all subjects will receive a monthly study newsletter that will provide information about practices to promote healthy living drawn from NIA's Go4Life program. The e-newsletters will be sent by local site coordinators.

Immediate Participation Group Procedures. Prior to the first group videoconference, Tele-Savvy hard materials (caregiver manual; workbook; journal; resource list) will be mailed to participants. Two days prior to the initial group videoconference (welcoming call), an email will be sent to participants asking them to view the orientation video lesson – the first lesson in the Canvas site. The initial group videoconference will begin a 43-day, six-week sequence of contact in which the daily video lessons are available to participants for asynchronous viewing in between the group videoconferences. The group videoconferences will be led by one or two trained facilitators, last approximately 75 minutes, and follow a fixed agenda and syllabus (see Appendix A). Vidyo allows all of the participants to see one another (they are also identified on the screen only by their first names); whoever is speaking is seen in the full-screen. Vidyo allows participants to ask questions directly or through a chat function. As with Savvy, an important function of the group meetings – following the introductory session – is to allow participants to demonstrate (or witness) successful implementation of effective caregiving strategies and to ask questions about the material presented during the week's daily videos or during the conference itself. The course syllabus and standardized slide decks structure each class in 15-20 minute increments: (1) Facilitators greet and check in with each of the CGs; (2) coaching and debriefing (e.g., hearing how (after the first week) CGs did with the homework, answering questions and/or

Timeline for Each Participating Cohort

responding to feedback about the week's material; (3) review of key points and concepts from the week's video sessions and introduction of new material (lecture, video vignettes and/or exercise; (4) reports of self-care activities (5) provision of homework assignments and adjournment. A project navigator will initiate and monitor each videoconference. The navigator will keep attendance records and troubleshoot the conferences, providing real-time assistance, should any participant need it; assistance is also logged.

